11.4 Additional unplanned analysis

After breaking the blind, we made the decision to additionally report PASDAS status and response variables that had been published since the inception of the trial. These were PASDAS very low disease activity, PASDAS moderate or good response, and PASDAS meaningful change value for improvement achieved (Y/N). These will be analysed according to the same methods indicated for the binary response variables i.e. adjusted estimates of effect size will be provided for binary secondary endpoints using multiple binary logistic regression; odds ratios and 95% confidence intervals will be presented. All analyses will control for the stratification factor and baseline values of the outcome where relevant. Two-sided significance at $p<0.05$ will be the criterion applied to indicate potential differences between treatment arms; however, as these comparisons were unplanned they will be considered exploratory.

In addition to these unplanned additional endpoints, unplanned additional descriptive summaries of total USGS and USPD will be presented, to help further illustrate that the lack of substantive change in US GLOESS (combined GS and PD score) was similarly observed for its sub-components.

Unplanned descriptive summaries of alternative definitions of US remission will be presented as the proportions achieving remission were very low, possibly because the criteria for joint remission were very strict.

Unplanned descriptive summaries of tender dactylitis count and 'any' dactylitis count will be presented to give further context to the LDI results, which only counts tender dactylitis.

12. SAFETY AND TOLERABILITY ANALYSES

12.1 Drug Exposure

- The following will be summarised descriptively within each treatment group
 - Total cumulative dose of golimumab
 - Total cumulative dose of methotrexate
 - Total steroid (IA/IM injection) dose received between weeks 0 and 12
- Summaries will also be presented corrected for patient-years of exposure

12.2 Adverse Events

12.2.1 Serious Adverse Events

Line listings of all SAEs will be provided in the end of trial report. Safety analyses will be conducted in the SS. A summary of incidence rates (frequencies and percentages) of SAEs by treatment group, System Organ Class, and Preferred Term will be prepared for the Safety Population. No statistical tests will be performed. The data will be displayed as number of subjects experiencing the SAEs, percentage of subjects, and number of SAEs. Data will also be corrected for exposure by 100 patient-years.

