## 8.18 Definition and Management of Disease Flare

Flare is defined as an increase in disease activity compared to previous assessment in a patient previously improving or stable, requiring a change in treatment. For patients on MDA, flare would be defined as a loss of MDA.

Flares of disease activity can be managed, at the investigators discretion, as follows:

- By altering analgesics.
- Steroids are only permitted at certain time points (weeks 8 and 12 and after week 24.).

**Prior to Week 24:** *Treatment Arms 1 and 2:* patients that are judged as clear non-responders (not achieving a PsARC response at week 12) or are intolerant of GOL/MTX may receive change in therapy (at the physician's discretion) but will be withdrawn from the interventional part of the study. A repeat WB-MRI may be performed at this stage (according to [section 8.6](#)). If they consent, patients will continue to be observed until the end of the study (week 52) and to undergo all the procedures as set per protocol timeline. Steroids IM/IA will be allowed only until week 12. From week 12 to week 24 only analgesics can be used.

- **After Week 24:** Subjects on both treatment arms will have IMP SC injections discontinued (GOL or placebo) at week 24. After this, participants will be observed for the remaining of the study period (i.e. until week 52). Disease flares occurring after week 24 and until week 52 will be treated according to normal clinical protocols and NICE guidelines.
- Other procedures at the time of flare: A response assessment will be carried out including a joint examination with swollen and tender joint counts/grading and patient and physician assessments of articular disease on Likaert scale for PsARC assessment; MDA (where applicable); blood testing for ESR, CRP; and patient-reported outcomes (disease activity and pain VAS, HAQ, BASDAI, ASQoL, SF-36, DLQI), physician's VAS (disease activity).

Blood samples will be taken for use in the biological sub-study.

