## 9.6 Recording and reporting of AEs

### 9.6.1 Recording and reporting of all AEs

Determination of AEs should be based on the signs or symptoms detected during the physical examination and on clinical evaluation of the subject, and should be assessed and recorded at every visit. Signs and symptoms must be recorded using standard medical terminology.

AEs and SAEs will be collected from first dose of protocol treatment until week 52 (visit 11). The Investigator must instruct the subject to report AEs and SAEs during this time period.

**All adverse events must be evaluated by a medically qualified and authorised member of the study research team, and graded (in terms of severity) in accordance with the Common Terminology Criteria for Adverse Events (CTCAE) (see [appendix 2](#)).**

During the time period specified above, the Investigator will:

- Record all AEs and SAEs on source documents.
- Record all AEs and SAEs in the eCRF for subjects who are not screen failures.
- Report all SAEs on a 'Serious Adverse Event/Expedited Report from a Clinical Trial'. Instructions on where to send this form will be provided by the Sponsor.

The Investigator must follow up on all AEs and SAEs until the events have subsided, returned to baseline, or, in case of permanent impairment, until the condition has stabilized whilst the subject remains under follow up as per study protocol. All adverse events that are still ongoing when the patient finishes study follow-up will be coded as 'ongoing' in the eCRF, after which time appropriate follow up will be organized as per standard clinical care.

The Sponsor will maintain detailed records of all AEs and SAEs reported by an Investigator in accordance with good clinical practice and applicable local regulations.

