### **11.3 General statistical considerations**

In general, analyses will be adjusted for the randomisation stratification factor(s) and baseline values of the outcome measure; 2-tailed tests will be performed and will be considered statistically significant if  $p < 0.05$ . A final analysis plan will be completed prior to the final data lock before unblinding. Any deviations from this plan will be documented in the final data report.

Unless otherwise specified, the last valid measurement before study medication administration will be utilized as the baseline value. In general, summary statistics [n (number of available measurements), arithmetic mean, standard deviation, median, minimum, and maximum] for quantitative variables and absolute and relative frequency tables for qualitative data will be presented.

Wherever possible the trial will be reported in accordance with the recommendations of the CONSORT (Consolidated Standards of Reporting Trials) statement (53-55).

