### 11.6 Safety analyses

Line listings of all SAEs will be provided in the end of trial report. Safety analyses will be conducted in the SS. The frequency of all SAEs during the study period will be presented for each treatment group separately. The data will be displayed as number of subjects experiencing the SAEs, percentage of subjects, and number of SAEs. Data will also be corrected for exposure by 100 patient-years. Quarterly listings of SAEs will be sent to Janssen Biologics.

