## **11.9 Determination of sample size and randomization method**

Using in-house unpublished data we estimated the minimum clinically important difference to be 0.7 units on the PASDAS; this is similar to a published value for smallest detectable difference of 0.8 units (11). We will aim to detect a difference of at least 1 unit between the treatment arms in this study. The standard deviation of PASDAS in the TICOPA MTX rapid escalation arm (56, 57) at 24 weeks (restricted to patients who remained on methotrexate throughout) was 1.57. Assuming  $\delta=1$ ,  $\sigma=1.57$ , at alpha=0.05 and 1-Beta=0.8 this would require 78 patients. Originally the sample size for the trial was adjusted to account for 10% drop-out, requiring a total of 88 (44 per group). However, because recruitment had been slower than anticipated, in part due to the SARS-CoV-2 pandemic, drop-out was reassessed once 76 participants had the opportunity to reach the primary endpoint. Only 4 (5%) had withdrawn from follow-up prior to that point. Therefore, the total required sample size was revised down to 84 (42 per group) i.e. allowing for 5% drop-out.

For the whole-body MRI subset, published rules of thumb for pilot studies indicate that between 12 and 30 patients per group should be included. We will aim to continue recruiting patients into the WB-MRI subset until there are at least 30 patients (15 per group) with scans available at both baseline and week 24, at which point WB-MRI will cease to be performed in the remaining patients.

To estimate the ICC between two repeated readings of the PASDAS composite index with a confidence interval of width 0.2, we would need 31 patients assuming the ICC is 0.85. For the patient's global assessment of disease activity VAS, which provides the greatest loading on the PASDAS score, ICC = 0.87(35). We will aim to obtain data from at least 31 patients.

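### The by-arm SAE table pools the double-blind weeks with the observational weeks up to week 52, and no planned table separates them

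*SAP*

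**What the plan says.** Protocol 9.6.1 sets the collection window: "AEs and SAEs will be collected from first dose of protocol treatment until week 52 (visit 11". Protocol 11.6 sets the reporting window: "The frequency of all SAEs during the study period will be presented for each treatment group separately". Protocol 8.18 treats the study period as ending at week 52 and states: "Subjects on both treatment arms will have IMP SC injections discontinued (GOL or placebo) at week 24". The schedule in protocol 8.6 calls the two parts double-blind randomised (Period 1) and observational (Period 2).

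SAP 12.2.1 describes the table: "The data will be displayed as number of subjects experiencing the SAEs, percentage of subjects, and number of SAEs". It adds line listings and a correction per 100 patient-years, without saying which time counts as exposure. It gives no split by period and no on-treatment window. SAP 12.2.2 tabulates AEs leading to withdrawal, without a window and without saying what the patient withdraws from. SAP 12.2.4 rules out any other AE analysis.

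After week 24, protocol 7.6.2 lets the investigator add DMARDs, and protocol 5.1 sends non-responders and flares in both arms to clinical protocols and NICE guidance. Exclusion criterion 1 uses DMARD to cover conventional and biological agents.

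**The concern.** Randomised injections are given in Period 1 only. In Period 2 neither arm is meant to be on them, patients may be on other treatment, and any SAE is still credited to the original arm. A reader who wants to know whether adding golimumab raised the SAE rate while it was being given cannot see that in the planned table. If the excess is confined to the dosing weeks, the later weeks add similar background events to both arms and pull the ratio, and the rate per patient-year, towards no difference. The SAP resolves efficacy by visit and ALT by week (SAP 12.4), but not SAEs.

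**Working it through.** **Number per arm.** Protocol 11.9 assumes a difference of 1, SD 1.57, alpha 0.05 (two-sided, protocol 11.3) and power 0.80. Per arm: 2 × (1.960 + 0.842)² × 1.57² / 1² = 2 × 7.849 × 2.465 = 38.7, so 39, or 78 in total. This matches the plan ("at alpha=0.05 and 1-Beta=0.8 this would require 78 patients"). With 5% drop-out, 39 / 0.95 = 41.05, so 42 per arm and 84 in total, also as stated. This supplies only the denominators. Neither document gives an SAE rate.

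**Patient time per arm, ignoring drop-out.** Period 1: 42 × 24/52 = 19.38 patient-years. Whole study: 42 patient-years. Period 1 is 24/52 = 46% of the tabulated time.

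**Pooled ratio.** Let RR be the assumed on-injection rate ratio, w1 and w2 the weeks on and off injections, and qG and qC the assumed shares of off-injection time that the golimumab and control arms spend on an equal-risk biologic. The background rate is taken as constant, and the excess as ending with dosing.

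Pooled ratio = [w1·RR + w2·(1 + qG(RR − 1))] / [w1 + w2·(1 + qC(RR − 1))]

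| Scenario, RR = 2 | Calculation | Shows as |
|---|---|---|
| 24 weeks on, no later biologic | (48 + 28)/52 | 1.46 |
| 28 weeks counted as on treatment | (56 + 24)/52 | 1.54 |
| Both arms 20% | 81.6/57.6 | 1.42 |
| Both arms 40% | 87.2/63.2 | 1.38 |
| Controls only 20% | 76/57.6 | 1.32 |
| Controls only 40% | 76/63.2 | 1.20 |

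On the first row's assumptions, an RR of 1.5 shows as 64/52 = 1.23 and an RR of 3 as 100/52 = 1.92.

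**Counts**, at an assumed control rate of 10 SAEs per 100 patient-years and RR 2:
- Period 1: 19.38 × 0.10 = 1.9 in controls, and 3.9 on golimumab.
- Period 2: 42 × 28/52 × 0.10 = 2.3 in each arm.
- Overall: 4.2 against 6.1. The difference is 1.9 in Period 1 and 1.9 overall.
- Patients with an SAE, from 1 − exp(−rate × time): 4.5% against 8.8% in Period 1 (4.3 points), and 9.5% against 13.6% overall (4.1 points).

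**Patient-year correction.** In Period 1 the assumed rates are 10 and 20 per 100 patient-years, a difference of 10.
- With 52-week follow-up as denominator, the rates are 4.20/42 = 10.0 and 6.14/42 = 14.6. The difference is 4.6, which is 46% of 10.
- With injection time as denominator and all SAEs as numerator, they are 4.20/19.38 = 21.7 and 6.14/19.38 = 31.7. The difference returns, but both rates are inflated by off-injection events and the ratio is still 1.46.

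Neither denominator recovers the Period 1 comparison.

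**Where the boundary lies.** Protocol 5.1 (for golimumab) and 8.18 (for both arms) discontinue injections at week 24. The schedule in 8.6 marks a study-drug administration at week 24, section 8.13 lists dispensing of study drug at that visit, and section 7.10 has patients in MDA continuing their allocated treatment. These passages conflict and must be reconciled. They decide whether the off-injection time is 28/52 (54%) or, with one more four-week interval, 24/52 (46%).

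**The case against.** The strongest reply is that the planned outputs are counts and percentages with no test and no ratio, and that the absolute excess in these hardly moves: about 1.9 SAEs either way, and 4.3 against 4.1 percentage points. That stands. The dilution concerns ratios and rates per 52-week patient-year. The count difference shrinks only if controls start a treatment that carries risk.

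A ratio of 1 straight after week 24 is also an assumption. The protocol's contraception and live-vaccine precautions run for 6 months after the last dose (inclusion criterion 5, exclusion criterion 22), so the plan itself allows for effects beyond dosing. Carry-over would lessen the dilution, and a table confined to Period 1 could miss late events. This is why the overall table should stay.

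SAEs are line-listed, so with few events a reader could rebuild the split if onset dates are shown. That mitigates the point but is not a planned comparison. Reporting to week 52 by randomised arm also suits a treatment-strategy question, but it answers a different question from risk while on golimumab.

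A reader might infer that only controls start biologics after week 24, giving 1.32 to 1.20. The documents do not support that asymmetry. The same routes are open to both arms, no passage names a later biologic for controls, and protocol 8.18 allows a change of therapy in either arm even before week 24.

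A reader might also infer that the AE-withdrawal table is diluted in the same way. Withdrawal from study injections cannot occur once they have ended, so those events fall mainly in Period 1. The gap in SAP 12.2.2 is that withdrawal is undefined.

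**Conclusion.** The point holds for the SAE table. Collection runs to week 52, protocol 5.1 and 8.18 end injections at week 24, the table pools both periods by arm, and no other AE analysis is planned. If the excess ends with dosing, a true ratio of 2 would show as about 1.46, or between 1.38 and 1.54 under the alternative boundary and the both-arms uptake scenarios. The pooled rate difference on 52-week patient-years would be 46% of the on-injection difference.

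It does not follow that a golimumab excess will be hidden. The dilution is conditional, the absolute count difference survives unless controls cross over, and carry-over works the other way. Nor is this the only safety comparison by arm, since ALT is summarised by visit. With roughly 1 to 8 SAEs expected per arm on injections (control rates of 5 to 20 per 100 patient-years, RR 2), any split is descriptive. It is a cheap improvement to a stated tabulation rule and does not threaten the trial's conclusions.

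**What to change.** 1. Reconcile protocol 7.10, 8.6 and 8.13 with 5.1 and 8.18 on whether study drug is given or continued at week 24, so that the period boundary matches actual exposure.
2. In SAP 12.2.1 and protocol 11.6, present the SAE table by arm for Period 1, Period 2 and overall, each with its own matching patient-years. Identify the double-blind period as the randomised on-treatment comparison, and keep the overall table so that late events are not lost.
3. Flag SAEs with onset after a new DMARD or biologic was started, in either arm.
4. In SAP 12.2.2, state whether withdrawal means from study injections, methotrexate or the study. Split that table by period only if it covers more than study injections.
5. Label the split as descriptive and, because the current SAP version postdates unblinding, as a post-unblinding addition, as SAP 11.4 does for its own additions.

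No new data collection should be needed: adverse events and concomitant medication are reviewed at every visit after baseline. The case report forms are not in the documents, so confirm that onset dates are recorded. The cost is some reprogramming and small counts per cell.

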12.2.2 Adverse Events Leading to Withdrawal

A summary of incidence rates (frequencies and percentages) of AEs leading to withdrawal, by treatment group, System Organ Class, and Preferred Term, will be prepared for the Safety Population. No statistical tests will be performed.

A data listing of AEs leading to withdrawal will also be provided, displaying details of the event(s) captured on the CRF.

12.2.3 Deaths

If any patients die during the study, relevant information will be supplied in a data listing, and appropriate SAE narratives.

12.2.4 Other AE Assessments

No additional Adverse Event analysis is planned.

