### 4.3 Safety variables

- Number of patients experiencing SAEs and AEs.
- Any clinically significant worsening of a pre-existing condition.
- An AE occurring from overdose of an IMP, whether accidental or intentional.
- An AE occurring from abuse (e.g. use for nonclinical reasons) of an IMP.
- An AE that has been associated with the discontinuation of the use of an IMP.

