### **7.4.2. Administration of the trial drugs**

Golimumab (Simponi®) should be injected subcutaneously once every four weeks.

In patients weighing 100 kg or more at baseline, the starting dose of golimumab will be 100 mg four weekly to be continued for the duration of the interventional period (week 0 to 24), even in cases of subsequent intentional weight loss.

In these cases, the investigators, taking into account the increased risk of certain serious adverse drug reactions with the 100 mg dose compared with the 50 mg dose (see [section 7.7](#) and [section 7.8](#)) will perform regular monitoring as specified in the summary schedule of study assessments ([section 8.6](#)).

The IMP will be administered by a suitably qualified and authorised member of the research team (i.e. study doctor or nurse) in an outpatient clinic setting within The Leeds Teaching Hospitals NHS Trust.

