## **7.5 Prior and concomitant illnesses**

Any concomitant diseases not included in the exclusion criteria are to be controlled using appropriate medication before the patient enters the study and if medically appropriate, the medication is to be continued during the entire study period. Concomitant medical conditions, any relevant medications, and any changes to both of these will be documented appropriately in the eCRF. Any new illness or worsening of a previous medical condition is to be recorded as an AE.

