3.3.3 Safety variables

- Number of patients experiencing SAEs and AEs.
- Any clinically significant worsening of a pre-existing condition.
- An AE occurring from overdose of an IMP, whether accidental or intentional.
- An AE occurring from abuse (e.g. use for nonclinical reasons) of an IMP.
- An AE that has been associated with the discontinuation of the use of an IMP.

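### The SAP plans no by-arm count of patients with any adverse event, although it lists that count as a safety variable

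*SAP*

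**What the plan says.** **Variable list.** The first safety variable in SAP 3.3.3 is "Number of patients experiencing SAEs and AEs", and protocol 4.3 has the same item. Both lists go on to "Any clinically significant worsening of a pre-existing condition", AEs from overdose or abuse of an IMP, and AEs associated with stopping an IMP.

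**Data collection.** Protocol 9.6.1 tells the investigator to "Record all AEs and SAEs in the eCRF for subjects who are not screen failures". Events are collected from the first dose of protocol treatment to week 52 and graded by CTCAE. Protocol 7.5 adds: "Any new illness or worsening of a previous medical condition is to be recorded as an AE".

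**Planned analysis.**
- SAP 12.2.1: SAEs by treatment group, System Organ Class and Preferred Term, with patients, percentages, events and a rate per 100 patient-years.
- SAP 12.2.2: "A summary of incidence rates (frequencies and percentages) of AEs leading to withdrawal, by treatment group", again by class and term, plus a listing.
- SAP 12.2.3: a listing and narratives for deaths.
- SAP 12.2.4: "No additional Adverse Event analysis is planned".
- Protocol 11.6: by-arm frequencies for SAEs only.

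**The concern.** A variable that both documents declare, and for which data are collected through the whole trial, has no planned output for half of its content. The SAE half is analysed and the AE half is not. SAP 12.2.4 is also more than a silence. It states that the AE analysis ends there, and a programmer working from section 12 would stop at that point.

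What is at stake is the description of harm. The trial adds a biologic to methotrexate in patients who have had no DMARD. A non-serious event that does not lead to withdrawal, such as a mild infection, would appear in no planned by-arm AE summary. A reader of the report could not set the overall frequency of adverse events in one arm against the other.

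**Working it through.** No figure in the plan is in dispute, so the main check sets the passages side by side.

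| Event category | Recorded? | By-arm AE summary planned? |
|---|---|---|
| SAEs | Yes (protocol 9.6.1) | Yes (SAP 12.2.1, protocol 11.6) |
| AEs leading to withdrawal | Yes | Yes (SAP 12.2.2) |
| Deaths | Yes | Listing and narratives (SAP 12.2.3) |
| Non-serious AEs not leading to withdrawal | Yes | None |
| Patients with any AE | Derivable from the above | None, although listed in SAP 3.3.3 and protocol 4.3 |

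Worsening of a pre-existing condition is recorded as an AE (protocol 7.5), so it belongs to the same gap and needs no separate argument. AEs from overdose or abuse belong there too, but are likely to be few: protocol 7.4.2 says "The IMP will be administered by a suitably qualified and authorised member of the research team", and protocol 9.2 has overdose reported as for an SAE. Events due unequivocally to progression of the arthritis or lack of response are not recorded as AEs (protocol 9.5.1), so an any-AE count would not contain them.

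**Other outputs that might fill the gap.**
- SAP 12.4 tabulates by arm the patients with laboratory values above the normal range, before versus after. An abnormal laboratory finding can be an AE (protocol 9.1), so this covers part of the gap. It does not count patients with AEs, and it says nothing about clinical events.
- SAP 9.1 gives discontinuations by treatment and main reason. These are dispositions, not AE counts.
- Protocol 11.3 promises frequency tables for qualitative data in general, but names no AE table. SAP 12.2.4 is later and specific.

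**Patient-years (minor).** SAP 12.1 and 12.2.1 and protocol 11.6 correct for exposure in patient-years without defining it. The IMP period is 24 weeks and AE collection runs to week 52. Inputs for illustration: 42 patients per arm (SAP 6), all treated and fully followed, and a 52-week year.
- 24-week reading: 42 × 24/52 = 19.4 patient-years per arm.
- 52-week reading: 42 × 52/52 = 42.0 patient-years per arm.
- Ratio: 52/24 = 2.17.
- One SAE in an arm: 100/19.4 = 5.2, or 100/42.0 = 2.4, per 100 patient-years.

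Counts and percentages of patients are the same under either reading.

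**The case against.** **The table is still allowed.** SAP 12.2.4 says only what is planned. SAP 2 and 5.2 permit unplanned analyses if they are identified. This stands. A reader might infer that the SAP rules out an any-AE table, and the text does not support that. What remains is that a variable named in advance depends on a discretionary, post hoc table.

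**The SAP does not fall short of the protocol's analysis section.** Protocol 11.6 plans by-arm output for SAEs only, and the SAP adds AEs leading to withdrawal. This also stands. The mismatch lies between the variable lists and the analysis sections, in both documents. It is not a departure of the SAP from the protocol.

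**Some non-serious events do reach a by-arm table.** The laboratory tabulation in SAP 12.4 is one. So it would be too strong to say that nothing outside SAEs and withdrawals is shown by arm, but the tabulation does not replace the missing count.

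**The undefined exposure term is small.** The SAE event window is given, no test or comparison of rates is planned, and with 1:1 allocation and similar follow-up the 2.17 factor rescales both arms about equally. This is right, and the point is only a clarification. There are also more than two readings: methotrexate continues for the whole study (protocol 7.1), and patients taken off study treatment are still followed to week 52 (protocol 7.10).

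**Conclusion.** The gap is real and should be closed. A declared safety variable, the number of patients with AEs, has no planned by-arm output, and SAP 12.2.4 states that none will be added. Two AE categories, SAEs and AEs leading to withdrawal, have a by-arm AE summary.

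The number of events left unsummarised is unknown, because the documents report no AE counts. The conclusion rests on the text alone and needs no assumed event rate. It does not touch the primary analysis, any test or any efficacy conclusion.

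Two stronger readings are not supported. The SAP does not prohibit the table, and the undefined patient-years are not a second finding. The 2.17-fold range assumes 42 fully followed patients per arm and concerns only the scale of an untested descriptive rate.

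**What to change.** Replace the sentence in SAP 12.2.4 with wording such as:

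*In the Safety Population, the number and percentage of patients with any AE, and the number of AEs, from first dose to week 52 will be tabulated by treatment group. The table is descriptive and no tests will be done. It was added after unblinding.*

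A split by maximum CTCAE grade is optional, since AEs are already graded. Tables by class and term for all AEs, separate rows for overdose or abuse, and a split by study period go beyond what the conflict requires.

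The cost is one descriptive table from data already in the eCRF, with no change to trial conduct. The downside is that it is a post-unblinding addition, so it must be labelled as one and stay descriptive. SAP v4.0 already does this for the summaries in 11.4.

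Optional clarification in the same edit: state in SAP 12.1 and 12.2.1 whether patient-years means time on IMP or follow-up time, and take the events and the patient-years of each rate from the same window.
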